- Occurrence of aspiration events requiring extended observation/monitoring, unplanned therapeutics, and/or hospital admission

Secondary Outcomes:

- Presence of any solid food
- Presence of moderate liquid content
- Increased RGC defined as any amount of solid content or $> 0.8 \text{ mL/Kg}$ of fluid content (measured from the aspiration/suction canister).
- Aspiration events up to 48 hours after endoscopy
- Differences in primary and secondary outcomes between different medications

Inclusion Criteria:

- Patients using incretin-based therapies at a stable dose for more than 1 month.
- Understand the study procedures and will be able to provide written informed consent to participate in the study.
- Patients scheduled for outpatient esophagogastroduodenoscopy (EGD), combined EGD and colonoscopy, endoscopic ultrasound (EUS), or endoscopic retrograde cholangiopancreatography (ERCP) under monitored anesthesia care (MAC) or moderate sedation.

Exclusion Criteria:

- Documented history of gastroparesis (based on a 4-hour solid-phase gastric emptying study)

- Known history of achalasia
- Surgical or genetically altered foregut anatomy
- Known gastric outlet obstruction or pre-procedure imaging suggestive of gastric outlet obstruction.
- Patients who did not follow the standard NPO (nil per oral) instructions.
- Patients who have planned endotracheal intubation (ETT) during their upper endoscopy procedure (EGD, EUS, or ERCP).
- Ongoing opiate use
- Unable or unwilling to give written consent

Randomization:

- Patients will be randomly assigned to either continue incretin-based therapy as prescribed (“continue” group) or to hold therapy as outlined in the ASA guidance recommendations (“hold” group).
- Simple randomization will be applied post-enrollment, utilizing REDCap serial numbers with pre-determined interventions (“continue” vs. “hold”). The randomization table of allocation will be completed by a statistician on REDCap to ensure concealed allocation.

Study Operation:

- The candidates for the study will be determined either during the gastroenterology clinic visit OR based on review of records by a member of the research team of patients scheduled for upper endoscopy, EUS, and ERCP cases three to four weeks in advance
- Patients’ invitation
 - For patients who are scheduled for the procedure through the gastroenterology clinic, the patient’s clinic provider will invite the patient for the study during the office visit or with a phone call.

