- An investigator or research coordinator will contact the invited candidates over the phone 2-4 weeks before the scheduled procedure. The study purpose, intervention, adverse events, and consenting process will be discussed over the phone. The encounter will be documented in the patient chart as a phone encounter.
- Subjects interested in the study will be provided with consent through MyChart Electronic consent or DocuSign with instructions to complete online consent signing.
- After all parties complete the consent, a randomization of the study intervention will be done through Redcap.
- A follow-up phone call will be made to communicate the instructions to the participants.

Rational for electronic consent (E-consent)

The study is not feasible with conventional consent, especially for open access procedures for the following reasons:

- The duration for participant involvement in the study is short, and the study intervention is only applied one week before the procedure, which would make it impractical to bring the patient for an extra encounter and would decrease the chance for enrollment.

- Many procedures are scheduled in an open-access fashion, which means that the patient is scheduled for the procedure by a provider other than the performing physician and/or from a different department.
- The intervention for the study must be completed one week before presenting to the procedure, which requires that the patient be enrolled before the procedure date.

Sample Size Determination:

- Previous retrospective studies indicate that 5-7% of GLP-1RA users have increased RGV compared to less than 0.5% in non-users.
- If there is a significant difference in favor of the experimental (“hold”) group of 7%, then 120 patients are needed (60 in each group) to be 80% certain that the upper limit of a one-sided 95% confidence interval (or equivalently a 90% two-sided confidence interval) will exclude a difference in favor of the standard group of more than 3% (the non-inferiority limit) using Farrington-Manning’s score test.
- Because estimates from previous retrospective studies are for the outcome of residual gastric volume, they may not accurately reflect our primary outcome, which is a more pragmatic and clinically useful outcome. Therefore, we plan to conduct an interim analysis at 20% recruitment and may adjust sample size if necessary, based on point estimates derived from the interim analysis.

Study Variables

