Date of birth, gender, race, body mass index (BMI), type of incretin-based therapy used, incretin therapy dose, pre-endoscopy clinical symptoms, presence of diabetes, last HbA1c if available, detailed endoscopic reports, gastric residual content on endoscopy, and RGC-related events as described above. Please refer to the data collection sheet for details of the variables above.

Study Statistics

The Statistics will be done with the help of a Cleveland Clinic statistician. Data will be extracted in deidentified form directly from Redcap for analysis.

Once data has been collected, we will use STATA version 14.1 (STATA Corp, College Station, TX, USA) for statistical analysis. We will use statistics of central tendency (mean, median, and mode) for most values. Data normality will be tested using Kolmogorov-Smirnov test. We will use Pearson’s chi-square tests for categorical variables and T-test for continuous variables. A P-value of < 0.05 will be considered significant for all statistical analyses. The primary outcome will be calculated using chi-square or Mann-Whitney test. For the primary outcome, an intention-to-treat analysis will be utilized.

Interim Analysis and Data Monitoring Committee (DMC)

The study DMC will include the following: The gastroenterology program director at Weston, a gastroenterologist, and a Cleveland Clinic statistician. Meetings will be held at 20%, 50, and 100% of recruitment to ensure data security compliance, appropriate rate of recruitment, and study adverse events monitoring. A report of each meeting will be sent to the IRB. The DMC will not be blinded for study groups. Interim analysis will be conducted after 20 and 50% of recruitment on the second DMC meeting, and the study will be stopped if inferiority is confirmed.

Data Security

Data, including patient information and consent, will be stored electronically in the Redcap system\DocuSign which is password-protected and on the secure Cleveland Clinic network. If physical paper sheets were used, the physical paper sheets' information would be transferred to Redcap and shredded on the day of data gathering.

Possible Harm to Subjects and Adverse Events

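### The sample size may be changed after 24 patients (about 0.9 events expected) with no written rule; re-sizing by arm could cut it after one event and lift the one-sided error to about 6.5-7.3%

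*Combined protocol and SAP*

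**What the plan says.** Sample Size Determination plans 120 patients (60 per arm) for 80% power with a one-sided 95% limit, a non-inferiority limit of 3% and the Farrington-Manning score test. Its rates come from earlier work: "Previous retrospective studies indicate that 5-7% of GLP-1RA users have increased RGV compared to less than 0.5% in non-users". It then doubts that those rates fit the composite endpoint, since "they may not accurately reflect our primary outcome, which is a more pragmatic and clinically useful outcome". For that reason it adds a look at 20% recruitment, after which the team "may adjust sample size if necessary, based on point estimates derived from the interim analysis".

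The section on interim analysis and the DMC says "The DMC will not be blinded for study groups". Its only decision rule is to stop if inferiority is confirmed. On timing it says "Meetings will be held at 20%, 50, and 100% of recruitment", and also "Interim analysis will be conducted after 20 and 50% of recruitment on the second DMC meeting".

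Study Statistics says "The primary outcome will be calculated using chi-square or Mann-Whitney test". Under Randomization, "Simple randomization will be applied post-enrollment". No section says how interim estimates become a new sample size, whether the size may fall, what bounds apply, or how the 5% error is kept.

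**The concern.** A re-sizing rule is harmless or harmful depending on what it uses. If it uses only the total event count, the final test is affected little. If it uses the observed difference between arms, the final size depends on the treatment comparison, and an ordinary final test need not keep its nominal level. The plan leaves both open, at a look where one event more or less changes the answer several-fold. At stake is the primary conclusion: hold could be declared non-inferior at more than the stated 5% error, or the trial could be cut well below 120 because of one patient. A rule settled after an unblinded committee has seen the counts cannot credibly repair this.

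**Working it through.** **Inputs.** From Sample Size Determination: one-sided 5% (z = 1.645), 80% power (z = 0.842), limit 3%, continue rate 7% (range 5-7%), 60 per arm, look at 20%. Hold is taken as 0.5%, the non-user rate. Assumed here because the plan gives no rule: raw rates go straight into the formula; equal arms (12 each at the look); a floor of 13 and a maximum of 120 per arm; the maximum is used when no finite size exists.

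**Formula.** n per arm = [(1.645 × s0 + 0.842 × s1) / (0.03 − (pH − pC))]², where s1² = pH(1 − pH) + pC(1 − pC), and s0 is the same expression at the maximum-likelihood rates constrained to differ by 3%.

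**Plan's own figure.** For 0.5% vs 7%: s0 = 0.310, s1 = 0.265, denominator 0.095. n = (0.733 / 0.095)² = 59.5, so 60 per arm and 120 in all. The plan's figure reproduces (with a 6.5-point difference; the text says 7%).

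**Size of the look.** 0.20 × 120 = 24 patients. Expected events: 12 × 0.07 + 12 × 0.005 = 0.90 (0.66 at a 5% continue rate).

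**Re-sized n per arm if used by arm** (chance at 7% vs 0.5%):

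| Events hold / continue | n per arm | Chance |
|---|---|---|
| 0 / 0 | 88 | 39% |
| 0 / 1 | 46 | 36% |
| 0 / 2 | 26 | 15% |
| 1 / 1 | 1,066 | 2% |

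Example, 0 / 1: s0 = 0.324, s1 = 0.276, denominator 0.03 + 1/12 = 0.1133; (0.766 / 0.1133)² = 45.7, so 46. For 0 / 0: s0 = √(0.03 × 0.97) = 0.1706, s1 = 0; (0.2806 / 0.03)² = 87.5, so 88. Over all outcomes, n falls below 60 with probability about 55%.

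**One-sided error**, by exact two-stage enumeration with the true hold rate set to continue + 3% and an unadjusted Farrington-Manning test at the end:

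| Continue rate | Fixed 60 | By arm, 13-120 | By arm, may only fall (13-60) | Pooled option |
|---|---|---|---|---|
| 0.5% | 3.2% | 5.3% | 2.7% | 5.5% |
| 1% | 4.4% | 5.1% | 3.9% | 5.2% |
| 5% | 5.0% | 6.5% | 6.0% | 4.9% |
| 7% | 4.8% | 7.0% | 6.3% | 4.8% |
| 10% | 4.8% | 7.3% | 6.7% | 4.8% |

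The pooled option sets 88 per arm if the 24 patients have no events, and 60 otherwise. It applies the planned 0.5:7 split to the pooled rate: one event gives rates of 0.56% and 7.8%, hence 56 per arm, which the floor raises to 60. A floor alone is not enough: by-arm re-sizing that can only increase (60-120) still gives about 5.5% at a 7% continue rate.

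**Power.**

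| Hold vs continue | Fixed 60 | By arm, 13-120 | Pooled option |
|---|---|---|---|
| 0.5% vs 7% | 92.3% | 92.4% | 95.7% |
| 0.5% vs 5% | 84% | 88% | 91.4% |
| 2% vs 2% (assumed) | 25% | 34% | 33% |

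If n may only fall, power at 7% vs 0.5% is 87.3%, still above the planned 80%.

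**Not modelled.** The stop for inferiority, which can only lower the error, and the chi-square or Mann-Whitney test. The tables assume equal arms. Simple randomization was simulated separately for the pooled option: error 3.5-5.0%, against 2.3-5.0% for a fixed 120 patients.

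**The case against.** The strongest reply is that the harm is conditional. The text is permissive. It does not say that raw rates from 12 patients per arm replace the planning rates, that the size may fall, or that the committee does the re-sizing; the stated purposes of its meetings do not include sample size. A sensible statistician might never cut the trial. All of this stands, so the finding is that the plan permits these outcomes, not that it prescribes them.

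The cuts are also less damaging than they look. A fixed trial of 46 or 26 per arm has 75% or 50% power at 7% vs 0.5%. Given the counts that would trigger those cuts, however, the chance of success is 84% or 95%, against 96% or 98.5% if the size stays at 60.

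The pooled rule has weaknesses too. At continue rates of 0.5-1% its error (5.2-5.5%) exceeds that of a fixed 60 and slightly exceeds that of by-arm re-sizing. Those low rates matter, because the plan itself doubts its planning rates. The rule fixes the split in advance, so it cannot learn the difference between arms. A by-arm rule that only increases, and stays at 60 when the estimate is beyond the limit, gives 5.0-5.5% (maximum 120) and is a fair competitor. These points limit what can be claimed for any one rule; they do not remove the need to write one.

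**Conclusion.** The concern holds in a bounded form. The plan allows its size to change on about 0.9 expected events with no rule, and an unblinded committee makes by-arm use possible. If that happened, the one-sided error would be about 6.5-7.3% at continue rates of 5-10% with assumed limits of 13-120 per arm, or 6.0-6.7% if the size may only fall, against 4.8-5.0% for a fixed 60.

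Three stronger readings might be inferred and are not supported:

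- That the trial will be re-sized by arm: the documents do not say so.
- That the error rises everywhere: at continue rates of 1% or less, rules that only reduce the size do not raise it. Errors up to 7.8% appear only with an assumed maximum of 300 per arm, five times the plan.
- That power is lost overall: with both increases and decreases, average power is not reduced.

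The error figures rest on the Farrington-Manning test, equal arms, mechanical use of the raw rates, and no stop for inferiority. Importance: should be changed. Confidence: medium, because the size of the effect depends on limits that the plan does not give.

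**What to change.** Before the look, write a single re-sizing rule that uses only the blinded pooled event count, is applied by someone given only that total, never goes below 120 patients, keeps the 3% limit, and states the assumed split and a maximum.

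One option under the planned 0.5:7 split is 88 per arm (176 patients) if there are no events among the first 24, and otherwise 60. State its limits with it:

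- Error is close to 5%, not strictly at it (see the table above).
- At 7% vs 0.5% it adds 0.39 × 56, about 22 patients on average, and at most 56.
- It depends on the split. A 0.5:5 split gives 88 and 61 per arm for zero and one event; 0.5:2 gives 88 and 89.
- It helps little if the arms do not differ: 2% vs 2% would need 334 per arm.

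Name the Farrington-Manning test as the final primary test in Study Statistics, in place of chi-square or Mann-Whitney. Reconcile the two sections on timing: one re-sizes at 20%, while the other can be read as placing both interim analyses at the second, 50% meeting. Each analysis needs one stated time. Beyond the possible extra patients, the cost is protocol wording.

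### Pearson's chi-square, with no exact alternative, is the stated test for comparing rare outcomes between medications, where it can call one isolated event a significant drug difference

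*Combined protocol and SAP*

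**What the plan says.** Secondary Outcomes lists "Differences in primary and secondary outcomes between different medications". Study Statistics assigns Pearson's "chi-square tests for categorical variables and T-test for continuous variables" and adds: "A P-value of < 0.05 will be considered significant for all statistical analyses". It names no exact test and no minimum expected count. The plan does not say whether each drug is set against all others, drugs are compared in pairs, or one overall test is used. Drug type is among the Study Variables, but neither the number of drugs nor the patients per drug is given.

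Sample Size Determination states "then 120 patients are needed (60 in each group) to be 80% certain" and quotes earlier studies in which "5-7% of GLP-1RA users have increased RGV compared to less than 0.5% in non-users". It warns that, for the trial's own composite, "they may not accurately reflect our primary outcome, which is a more pragmatic and clinically useful outcome".

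**The concern.** Pearson's P-value relies on a large-sample approximation. When a drug has few users and the outcome is rare, the expected number of events in that drug falls well below 1 and the approximation can fail badly. A single aspiration or abandoned examination could then be reported as a significant difference between drugs when chance explains it easily. In a trial about periprocedural safety, that could be read as drug-specific safety evidence.

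**Working it through.** **Inputs.** N = 120, 60 per arm, and planning rates of 7% and 0.5% (Sample Size Determination). Threshold P < 0.05 (Study Statistics). Numbers of users per drug are my assumption throughout.

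**The plan's own figure.** Farrington-Manning with 7% against 0.5%, a 3-point margin, one-sided 5% and 80% power gives 59.5, so 60 per group, which reproduces the stated 120.

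**Expected counts.** 60 × 0.07 + 60 × 0.005 = 4.5 events, an average rate of 4.5/120 = 3.75%. A drug with n users expects 4.5n/120 events. For an assumed mix of 60/25/20/10/5 this gives 2.25, 0.94, 0.75, 0.38 and 0.19. For 60/30/20/10 it gives 2.25, 1.12, 0.75 and 0.38. Rarer outcomes give smaller counts.

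**One event in the whole trial, drug versus the rest.** If the event falls in a drug with n users, Pearson's statistic is N(N − n) / [n(N − 1)], and 3.84 is needed on 1 degree of freedom. The exact P-value in the cases below is n/120.

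- n = 24: 120 × 96 / (24 × 119) = 4.03, P = 0.045; exact 24/120 = 0.20.
- n = 25: 120 × 95 / (25 × 119) = 3.83, P = 0.0503, not significant.
- n = 12: 120 × 108 / (12 × 119) = 9.08, P = 0.003; exact 12/120 = 0.10.

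**More events in total.** With one event in the drug and the others elsewhere, the largest n that is significant falls to 11 (two events in total), 7 (three), 5 (four) and 4 (five). At n = 24 with two events in total, P = 0.285.

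**Overall test across drugs, one event in total.** The statistic is the same but has more degrees of freedom. The largest n is 17 for three drugs, 13 for four and 11 for five. Example: four drugs, event in the smallest group of 10: 120 × 110 / (10 × 119) = 11.09 on 3 degrees of freedom, P = 0.011, against an exact 10/120 = 0.083.

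**Overall false-positive rate.** For each possible total number of events, I enumerated every split across drugs under no drug effect (hypergeometric), added up those with Pearson P < 0.05, and weighted by Binomial(120, event rate).

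| Assumed users per drug | 1% rate | 2% rate | 3.75% rate |
|---|---|---|---|
| 60/25/20/10/5, overall test | 7.8% | 8.4% | 6.7% |
| 100/15/5, overall test | 9.6% | 10.2% | 7.3% |
| 70/30/10/5/3/2, overall test | 10.2% | 12.2% | 11.4% |
| 24 versus 96 | 9.1% | 8.2% | 5.3% |
| 12 versus 108 | about 4% | about 4% | about 4% |
| 60/30/20/10, overall test | about 4.5% | about 4.5% | about 4.5% |

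The exact test stays below 5% in every row. For 24 versus 96 it is 1.0% at a 1% rate and 1.6% at 2%. For the two arms of 60, Pearson gives 4.2% at 3.75% and no more than about 5% at any rate up to 10%.

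**The case against.** A reader might infer from the one-event figures that any event in a drug with 24 or fewer users will be declared significant, and that the false-positive rate is 20%. The documents support neither. Both figures require that the event is the only one among 120 patients and that the drug is tested against all others pooled, a layout the plan does not specify. At the plan's rates of 7% and 0.5%, exactly one event in total has probability 4.6% (11.8% with 5% and 0.5%). The 20% is conditional on that; the unconditional error for a 24-patient drug peaks near 9% and is 4.1% at a 5% event rate. For a 12-patient drug it never exceeds nominal, despite the striking single-event P-value.

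It is also fair to say that the inflation rests on assumed drug mixes, and that the largest figure comes from a mix with groups of two and three patients. Any solid food, moderate liquid and increased gastric content are also compared between drugs and need not be rare. The comparison is the last-listed secondary outcome, is not randomised, and has no bearing on the primary conclusion. A statistician will assist with the analysis.

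All of this limits the size of the problem. It does not remove it: the plan states one test and one threshold, offers nothing for sparse tables, and schedules a comparison in which sparse tables are likely.

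**Conclusion.** The concern holds in a limited form. The prescribed test is unreliable for between-medication comparisons of rare outcomes. It can label a lone event significant when the exact probability is as high as 0.20, under the two conditions given above. Overall error is about 7-12% under assumed uneven mixes with very small groups at event rates of 1-3.75%, and about 9% for a single 24-patient drug at 1%. It is at or near nominal for milder mixes and for the two randomised arms. The actual drug mix and the rate of the composite are unknown, so the true inflation cannot be fixed from the documents. The risk is greatest for the rarest outcomes, such as aspiration. This is worth correcting but does not threaten the trial's main comparison.

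**What to change.** In Study Statistics, replace Pearson's chi-square for the between-medication comparisons with the Fisher-Freeman-Halton exact test (Fisher's exact test where only two groups are compared). Report each drug's event count, denominator and exact 95% confidence interval, so that a reader can see how little data lies behind any difference.

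The cost is one sentence. It needs no new data and leaves the sample size unchanged. The downside is that exact tests are conservative, so a true drug difference is somewhat harder to declare. The exact test would still flag a lone event in a drug with five users (5/120 = 0.042), which is one reason to show the counts as well as the P-value.

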Randomized trial of holding vs. continuing incretin-based therapies before upper endoscopy

Principal Investigator:

[name].

Email: [contact]

Address: [name]

Background:

Incretin-based therapies include GLP-1 receptor agonists (GLP-1RAs) and dual GLP1-RA and gastric inhibitory polypeptide (GIP) agonists. These drugs are commonly prescribed for diabetes and more recently, their use has risen exponentially as a primary therapy for weight loss. These medications can decelerate gastric emptying and diminish bowel motility by inhibiting peristalsis at the GLP-1 receptors situated in myenteric neurons. Therefore, there exists a theoretic potential for gastroparesis, retained gastric contents, perioperative regurgitation, and pulmonary aspiration syndrome, and this is a concern for anesthesiologists and patients taking these medications.

The American Society of Anesthesiologists recently released a consensus-based statement that recommends patients on daily dosing hold incretin-based therapy the day of the procedure, and those on weekly dosing hold the medication a week before the procedure. The evidence for these recommendations is based on retrospective studies and case reports, and therefore the conclusions may be overly prescriptive. Furthermore, holding incretin-based therapy poses a risk for worsening diabetes control and more importantly, could cause unnecessary delays in care if a patient's procedure is postponed because they failed to hold the medication based on the recent recommendations (1-3).

Study Objective:

To assess whether holding incretin-based therapy before endoscopy reduces the likelihood of clinically relevant Residual Gastric Volume (RGV).

Hypothesis:

Holding incretin-based therapy is non-inferior to continuing incretin-based therapy for reducing the risk of clinically relevant RGV.

Study design:

Randomized Non-Inferiority Controlled Trial.

Blinding:

Single-blind: endoscopist and anesthesia team will be blinded to study group assignment.

Primary Outcomes:

The primary outcome is clinically significant residual gastric volume defined as a composite of the following variables:

- Residual gastric volume that precludes adequate endoscopic examination
- Residual gastric volume that necessitates premature termination of the endoscopy procedure
- Need for endotracheal intubation due to stomach contents.

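### The primary analysis names tests of zero difference, so it cannot apply the 3-point non-inferiority criterion on which the trial is sized

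*Combined protocol and SAP*

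**What the plan says.** The combined protocol and SAP sets up a non-inferiority trial in three places.

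- **Study design:** "Randomized Non-Inferiority Controlled Trial".
- **Hypothesis:** "Holding incretin-based therapy is non-inferior to continuing incretin-based therapy for reducing the risk of clinically relevant RGV".
- **Sample Size Determination:** 60 patients per group give 80% certainty that the upper one-sided 95% limit ("or equivalently a 90% two-sided confidence interval") will "exclude a difference in favor of the standard group of more than 3% (the non-inferiority limit"), by the Farrington-Manning score test. Hold is the experimental group, so the standard group is continue.

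The endpoint is yes/no. Under Primary Outcomes, "The primary outcome is clinically significant residual gastric volume defined as a composite of the following variables".

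Study Statistics, the only section that prescribes the final analysis, says: "The primary outcome will be calculated using chi-square or Mann-Whitney test". It adds: "A P-value of < 0.05 will be considered significant for all statistical analyses". It gives no margin, no interval for the risk difference, no one-sided level and no rule for concluding non-inferiority. No other section supplies them.

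**The concern.** The hypothesis and the named tests address different questions. Write d for the risk of the primary outcome on hold minus the risk on continue.

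- **Non-inferiority criterion:** the null is d ≥ 3 points, and it is rejected when the upper limit falls below 3 points.
- **Pearson chi-square:** the null is d = 0. The 3-point limit does not enter.
- **Mann-Whitney on a yes/no outcome:** this is almost the same test as chi-square, so it does not fill the gap.

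Two analysts, one following Sample Size Determination and the other Study Statistics, can therefore reach different conclusions from the same data. A non-significant P could be read as showing that hold is not inferior when the data do not exclude a 3-point excess. Conversely, non-inferiority that the sizing criterion would accept could go unclaimed. The stated 80% power belongs to the margin criterion, not to the tests named for the primary outcome.

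**Working it through.** **Inputs.** From Sample Size Determination: 60 per arm, margin 3 points, one-sided 5%, 80% power, Farrington-Manning; retrospective rates of 5–7% in users and under 0.5% in non-users. From Study Statistics: chi-square, P<0.05. *Assumptions:* the plan gives no arm rates, so the rates below are assumed. It gives no sidedness for P<0.05, so two-sided is assumed. Chi-square is uncorrected.

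**1. Reproduce the plan's 60 per arm.** Take hold 0.5% and continue 7%.

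n = [(z₀.₉₅√V₀ + z₀.₈₀√V₁) / (d − 0.03)]²

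- d = 0.005 − 0.07 = −0.065.
- V₁ = 0.005×0.995 + 0.07×0.93 = 0.0701.
- V₀ uses the maximum-likelihood rates restricted to a 3-point difference (0.0658 and 0.0358): 0.0658×0.9342 + 0.0358×0.9642 = 0.0960.
- n = [(1.645×0.3099 + 0.842×0.2647) / 0.095]² = (0.7325/0.095)² = 59.5, so 60 per arm, with asymptotic power 80.4%.

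The planned number is thus a Farrington-Manning non-inferiority number. These rates differ by 6.5 points, not the stated 7. A literal 7-point gap gives 57 per arm (0.5% vs 7.5%) or 62 (1% vs 8%).

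**2. Apply both rules to the same tables, 60 per arm.**

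Chi-square: z = (p_H − p_C)/√[2p̄(1−p̄)/60]. Farrington-Manning: z = (p_H − p_C − 0.03)/SE, with SE from the restricted rates.

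*4 hold vs 4 continue.* The chi-square z is 0. The restricted rates are 0.0847 and 0.0547, so SE = √[(0.0847×0.9153 + 0.0547×0.9453)/60] = 0.0464 and z = −0.03/0.0464 = −0.65.

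*0 hold vs 1 continue.* The chi-square z is −0.0167/√(2×0.00833×0.99167/60) = −1.00. The restricted rates are 0.0382 and 0.0082, SE = 0.0274, and z = (−0.0167 − 0.03)/0.0274 = −1.71 (unrounded inputs).

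| Events, hold vs continue | Chi-square p | Farrington-Manning one-sided p | Upper 90% limit | 3-point criterion |
|---|---|---|---|---|
| 4 vs 4 | 1.0 | 0.26 | +8.3 points | not met |
| 0 vs 1 | 0.32 | 0.044 | +2.7 points | met |

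Similarly, 2 vs 2 gives p=1.0 and 0.20 (not met), and 0 vs 3 gives p=0.079 and 0.012 (met).

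**3. Enumerate all 61×61 tables.** Chi-square is significant in favour of hold in 1,355 tables, and all of these meet the 3-point criterion. Another 180 tables meet it without chi-square significance. A significant result favouring hold is therefore safe. The problem lies in the non-significant results, for which the plan has no rule.

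**4. How often the rules part, by exact binomial probabilities.**

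- *Hold truly 3 points worse* (assumed 8% vs 5%, or 10% vs 7%): chi-square is non-significant in 90–91% of trials; the margin criterion declares non-inferiority in about 5%.
- *Equal true rates of 5%:* chi-square is non-significant in 95% of trials; the margin criterion is met in about 18%.
- *Hold 0.5%, continue 7%:* chi-square is significant in 48%. In a further 44% the margin criterion is met but chi-square is non-significant. The sum, 92%, is the exact power of Farrington-Manning; the 80.4% in step 1 is its asymptotic value.

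**5. Power of the named test at 60 per arm.** At 0.5% vs 7%, p̄ = 0.0375. The normal approximation is Φ[(0.065√60 − 1.96√(2×0.0375×0.9625))/√0.0701] = Φ(−0.09) = 46.5%, against 48% exact. At a full 7-point difference, exact power is 61% (0% vs 7%), 53% (0.5% vs 7.5%) or 47% (1% vs 8%). Mann-Whitney (normal approximation with ties, no continuity correction) gives the same four values. At 0.5% vs 7%, two-sided chi-square would need 133 per arm for 80% power. This is power against zero difference, a different hypothesis from the one behind the plan's 80%.

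**The case against.** The strongest reply is that the margin and the Farrington-Manning test appear only as the basis for the sample size, so Study Statistics omits the criterion and does not reject it. It is true that the margin appears nowhere else. But the section goes beyond omission: it expressly names other tests for the primary outcome, and those tests cannot evaluate the stated hypothesis. Leaving the choice to the analyst is not safe either, because the DMC sees unblinded data at the interim looks and the rule should be fixed beforehand.

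Second, the Study Objective asks whether holding reduces the risk, which is a superiority question that chi-square would suit. That is fair, and chi-square can stay as a secondary comparison. It does not make chi-square a test of the non-inferiority hypothesis.

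Third, the plan nowhere says that a non-significant P will be taken as non-inferiority. This stands. The 90–91% figure is an error rate only under that reading. Without it, the cost is non-inferiority left unclaimed, not falsely claimed.

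Fourth, the power figures rest on assumed rates and a two-sided reading. This also stands. A one-sided chi-square raises power at 0.5% vs 7% from 46.5% to about 59% (normal approximation), but still has no margin. The 0.5% comes from non-users, and the plan itself warns that the retrospective rates may not reflect its primary outcome. The single-table examples need no assumed event rates.

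**Conclusion.** The concern holds: the primary analysis is wrong as written and must be corrected. The hypothesis and the sample size require that a 3-point excess on hold be excluded; the tests named for the primary outcome address zero difference only. At 60 per arm the two rules give different answers in both directions, as 4 vs 4 and 0 vs 1 show.

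That conclusion does not depend on assumed event rates. The frequency of disagreement does: 44% of trials at 0.5% hold vs 7% continue, with uncorrected two-sided chi-square. The direction of the comparison is taken from Hypothesis and Sample Size Determination as written. Whether it is the intended direction is a separate question.

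**What to change.** In Study Statistics, replace the sentence on the primary outcome with:

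> The primary analysis is the risk difference (hold minus continue) with its two-sided 90% Farrington-Manning score confidence interval. Non-inferiority of hold is concluded only if the upper limit is below 3 percentage points.

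Remove chi-square and Mann-Whitney as the primary analysis. State that the general P<0.05 rule does not govern the non-inferiority decision. Chi-square can keep its general role for categorical variables, including a secondary test of the superiority question in the Study Objective.

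The cost is a change of wording, with no extra patients or data. The text above covers the final analysis only; it does not address the interim looks or the possible sample-size adjustment.
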